Based on expert's knowledge, we find a 1 week lead in the functional recovery of the motor experimental group on the control group a clinically significant difference. With use of the mathematical model, the change in the PRWHE-score after 1 week after cast removal could be estimated. Next, the mean standard deviation of the PRWHE-scores over time was calculated. By dividing the change in the PRWHE-score by the mean standard deviation, the effect size was calculated. Now, the sample size could be calculated using the statistical power analysis software G*Power 3 (62).

Effect size calculation

The model describing the change in the PRWHE-score as result of natural recovery following a DRF, showed that 1 week after cast removal a decrease of 5.3 points on the PRWHE can be expected, which indicates improved function. This would mean that the experimental group would show an extra decrease of 5 points on the PRWHE, two weeks after cast removal.

The mean standard deviation was calculated using the following formula:

$$\sigma = \sqrt{\frac{n_x^2 s_x^2 + n_y^2 s_y^2 - n_y s_x^2 - n_x s_y^2 - n_x s_x^2 - n_x s_y^2 + n_y n_x s_x^2 + n_y n_x s_y^2 + n_x n_y (\bar{X} - \bar{Y})^2}{(n_x + n_y - 1)(n_x + n_y)}}$$

This provided a mean standard deviation of 26.13... points.

The effect size was calculated using the following formula:

$$ES = \frac{\mu_1 - \mu_2}{\sigma}$$

This provided an effect size of 0.20...

Settings for sample size calculation

Test Family: F-tests

Statistical test: Repeated Measures ANOVA, within-between interaction

Effect size: 0.20

Significance level $\alpha = 5\%$

Preferred power = 80%

Number of groups: 2

Number of measurements: 2

Other settings were kept as the default setting.

Sample size calculation

The effect size, preferred power, significance level and two-tailed testing were entered in

G*Power 3. Running the program resulted in a calculated sample size of 52 patients.

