7.6 Follow-up of subjects withdrawn from treatment

Patients who withdraw from the treatment will be followed-up. Because the patients are asked to enter the number of motor imagery sessions each day in a diary, it still provides information concerning the effectiveness of motor imagery training.

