9. STATISTICAL ANALYSIS

9.1 *Descriptive statistics*

Patient characteristics are presented using descriptive statistics for the potential confounding variables.

Data of the main outcome measure are of interval level of measurement. The ROM and grip strength are of ratio level of measurement. Hence, the descriptive statistics of these outcome measures are presented by the mean and standard deviation. Dexterity is measured using the SODA, and the data of this instrument are of ordinal level of measurement. Therefore, the descriptive statistics are presented by the median and range. Pain is measured using the VAS, which provides data of interval level of measurement. So, the descriptive statistics are presented by the mean and standard deviation.

9.2 *Univariate analysis*

The effectiveness of motor imagery training will be determined with use of a multivariate analysis for the parametric data (as described later in chapter 9.3). The non-parametric data are analyzed using a Mann-Whitney U test for each variable, to determine whether the groups are different. This test is also used when the data is not normally distributed.

9.3 *Multivariate analysis*

With use of a MANOVA, the difference between the experimental and control group will be determined for each measurement time and for each variable. There are two factors included in the analysis; a between factor 'group' and a within factor 'time'. The hypothesis is tested using two-tailed tests, with a significance level of 5%. The data of the patients in both groups will be analyzed using an intention to treat analysis.

9.4 *Interim analysis (if applicable)*

An interim analysis will be conducted to determine the effect of motor imagery training on hand function, dexterity, ROM, grip strength and pain. When the results of this analysis shows serious unwanted effects of motor imagery training, this study will be terminated.

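### Section 9.3 promises intention to treat, but its MANOVA with no missing-data method defaults to a complete-case analysis, and section 5.2 contradicts the promise outright

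*Combined protocol and SAP*

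**What the plan says.** Section 9.3 describes the main analysis: "With use of a MANOVA, the difference between the experimental and control group will be determined for each measurement time and for each variable". It names two factors, group (between patients) and time (within patients), and then adds: "The data of the patients in both groups will be analyzed using an intention to treat analysis".

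Section 9.2 sends the remaining outcomes elsewhere: "The non-parametric data are analyzed using a Mann-Whitney U test for each variable, to determine whether the groups are different". That covers SODA, which section 9.1 classes as ordinal, and any outcome that turns out not to be normally distributed.

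Three other sections bear on who is analysed:

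- Section 5.2 leaves out of the statistical analysis any patient who reports another intervention or treatment during the study.
- Section 7.5 replaces withdrawn patients so that the groups stay equal in size.
- Section 7.6 says: "Patients who withdraw from the treatment will be followed-up".

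The protocol does not mention missing outcome values, complete cases or imputation, and it does not define an analysis set.

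**The concern.** A conventional MANOVA needs a complete set of the outcome values entered for each patient. With time as a within factor, that means both T1 and T2. Unless the plan provides otherwise, a patient with a gap is deleted and her observed values go with her. The result would be a complete-case analysis carrying an intention-to-treat label.

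Gaps are foreseeable. There are two measurement times. Under section 7.3 the T1 PRWHE is taken by phone the day after the other T1 tests. Grip strength and range of motion are tested directly after cast removal, when pain may prevent a test. Patients who miss a visit or cannot do a test need not resemble the others, so deleting them can bias the group comparison as well as reduce power.

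The size of the problem depends on the model. With one model per outcome, a missed pinch test affects only that pinch outcome. With all outcomes in one joint model, it also removes the patient's PRWHE.

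**Working it through.** **1. The plan's own sample size.** Inputs from section 4.4: effect size 0.20, two-tailed α of 0.05, power 80%, 2 groups, 2 measurements, repeated-measures ANOVA with within-between interaction, other settings at default. I took the defaults to be a correlation ρ of 0.5 and no nonsphericity correction (assumption).

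λ = f² × N × m / (1 − ρ), with df1 = 1 and df2 = N − 2.

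For N = 52: λ = 0.04 × 52 × 2 / 0.5 = 8.32 and power = 0.807. At N = 50, power is 0.791, so 52 is the smallest even N that reaches 0.80. The stated 52 reproduces, and the same formula gives the power figures below. They take the 0.20 as it was entered and do not examine how it was derived.

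**2. Values per patient.** Parametric measures in sections 7.1.1 and 7.1.2, counting the injured hand only: PRWHE 1, range of motion 6, grips 4, VAS 2, total 13. At two times this is 13 × 2 = 26 values in one joint model. One model per outcome needs 2 values.

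**3. Patients lost.** The documents give no missing-data rate, so 0.5%, 1% and 2% of values are assumed, missing independently and without replacement of patients. With missing fraction p and c values required, the share lost is 1 − (1 − p)^c, and 52 × (1 − p)^c patients remain.

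| Assumed p | Model | Share lost | Patients kept of 52 | Power |
|---|---|---|---|---|
| 0.5% | one per outcome (c = 2) | 1 − 0.995² = 1% | about 51 | 0.80 |
| 1% | one per outcome | 1 − 0.99² = 2% | about 51 | 0.80 |
| 2% | one per outcome | 1 − 0.98² = 4% | about 50 | 0.79 |
| 0.5% | joint (c = 26) | 1 − 0.995²⁶ = 12% | about 46 | 0.76 |
| 1% | joint | 1 − 0.99²⁶ = 23% | about 40 | 0.69 |
| 2% | joint | 1 − 0.98²⁶ = 41% | about 31 | 0.58 |

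**4. Clustering.** If values go missing as whole time points, at 1% or 2% per time point, even the joint model loses only 1 − 0.99² = 2% or 1 − 0.98² = 4%. Independent missingness is therefore close to the worst case for the joint model.

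**5. Section 5.2 against section 9.3.** This needs no assumed rate. Section 5.2 removes patients for something that happens after allocation, while section 9.3 promises intention to treat. The two cannot both be followed.

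**The case against.** The strongest reply is that nothing in section 9.3 orders incomplete patients to be dropped. Listwise deletion is a usual software default and not a protocol rule, and intention to treat is chiefly about analysing patients in the group to which they were allocated. This stands. A reader might infer that a MANOVA can never be an intention-to-treat analysis. The documents do not support that, because on complete or imputed data the two are compatible.

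A reader might also infer that the MANOVA throws away the follow-up collected under section 7.6. It does not. A patient who stops the imagery but is measured at both times has complete data and stays in, so section 7.6 supports the intention-to-treat statement.

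Third, section 9.3 says the comparison is made for each variable, which may well mean one model per outcome. On that reading a missed pinch test leaves the PRWHE untouched and the losses are small. This also stands, as does the narrower scope: SODA and any non-normal outcome go to Mann-Whitney tests, which shrinks any joint model.

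Finally, replacement under section 7.5 would offset power lost through withdrawal. It would not remove bias, and it does not cover a patient who stays in the study but misses a test.

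What the reply does not answer is that the plan says nothing about missing outcomes. On either reading, a model with time as a within factor loses a patient who has only one of the two measurements.

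**Conclusion.** The point holds as a gap in the plan and a contradiction between two sections. As written, section 9.3 leads by default to a complete-case analysis of the parametric outcomes, the primary one included, while promising intention to treat. Section 5.2 contradicts that promise directly.

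The size is uncertain. With one model per outcome the loss is 1% to 4% of patients and power stays at about 0.79 to 0.80. With one joint model it is 12% to 41%, and power falls to between about 0.76 and 0.58. These figures rest on assumed missing rates, independent missingness, no replacement, a count of the injured hand only, and the plan's own effect size and assumed default correlation. It would be tempting to quote the joint-model losses as what the trial will suffer. The documents do not support that, because the wording allows separate models and values collected around one visit would tend to go missing together.

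**What to change.** For each parametric outcome, replace the MANOVA by a linear mixed model with group, time, group × time, the covariates of section 7.1.3 and an unstructured within-patient covariance. Fit it to all observed T1 and T2 values of every included patient, in the group to which she was allocated. Keep the planned Mann-Whitney test for SODA. This also settles whether the outcomes are modelled jointly or one by one.

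Define the analysis set in section 9.3 and reconcile section 5.2 with it, so that patients with co-interventions are not removed from an analysis called intention to treat.

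The cost is wording; no new data are needed. There are two limits. The mixed model is valid only if missingness depends on observed data alone, so add a simple sensitivity analysis for departures from that. It also still drops a patient whose covariates are missing, so those should be collected completely.

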10. ETHICAL CONSIDERATIONS

10.1 Regulation statement

We state that the study will be conducted according to the principles of the Declaration of Helsinki and in accordance with the Medical Research Involving Human Subjects Act (WMO) and other guidelines, regulations and Acts.

10.2 Recruitment and consent

The diagnose list of the Emergency department of the University Medical Center Groningen is checked daily for DRF. Within 48 hours after initial treatment, an information letter is sent to the patients who reach the inclusion criteria to inform them about this study and ask them for their participation. As explained in chapter 7.2, potential participants are already allocated to the experimental or control group, so the patients in the experimental group receive an information letter that is different from the information letter that the patients in the control group receive. In this letter, the patients are asked for their participation. When they are willing to participate, the patients return a signed informed consent. One week after initial treatment, the patients return to the hospital for a check-up appointment. At that moment, they have had 5-7 days to consider their participation. In the outpatient clinic, the patients who sent back a signed informed consent are asked to fill out the Vividness of Motor Imagery Questionnaire (VMIQ). The outcome of this test determines the final inclusion or exclusion of the patient. Patients who have an internal VMIQ-score > 72 are excluded, because this indicates that their ability to perform motor imagery is low. The patients with a VMIQ-score ≤ 72 are included. Patients allocated to the control group receive information about the measurements, the measurement times and the duration of the study. Patients allocated to the experimental group receive the same information about the measurements and duration, but also instructions to do motor imagery training. The patients in both groups will receive an information letter, but the patients in the experimental group also receive a letter that contains the instructions to do motor imagery training.

10.3 Objection by minors or incapacitated subjects (if applicable)

Not applicable.

10.4 Benefits and risks assessment, group relatedness

Benefits

DRF is a very common injury, especially in elderly women (1-5). In most conservatively treated cases, the patients are immobilized by a plaster cast for 4 to 6 weeks (7). Immobilization can lead to muscle atrophy (8-10) and contractures (11). Research has shown that immobilization or limb disuse can cause cerebral reorganization and decreased excitability of the motor cortex (27-29,38), and therefore, can lead to deteriorated motor performance (77). During motor imagery, partly the same cortical areas are activated as during execution of movement (34-37). So, motor imagery might prevent such neural changes as cerebral reorganization and decreased excitability (31). Many studies to determine the effectiveness of motor imagery training are conducted in stroke patients, and these studies show that motor imagery is effective in regaining arm function (49,50,53,78). By making the patients do motor imagery training during the immobilization period, it is expected that these patients have a better outcome when their cast is removed. Hereby, these patients might recover more quickly, and possibly reach a better final outcome.

Risks

The risk of participation in this study is negligible. Measuring function and pain with use of respectively the PRWHE and VAS which are questionnaires, is not harmful to the patient. The measurement of ROM and grip strength is already part of the regular treatment protocol of DRF. Therefore, the measurements conducted in this study to determine ROM and grip strength will not provide a higher risk than the regular treatment protocol. The SODA is a test concerning the performance during activities of daily living. It is performed after cast removal when the medical treatment is completed. From that moment, the patients are advised to use their injured hand again, so it is improbable that the SODA will lead to a higher risk than the regular procedure. There are no studies found that determined the risks of motor imagery training. However, because the motor imagery training does not contain motion, it is highly unlikely that the intervention will be harmful.

The patients are measured twice, directly after cast removal and 2 weeks after cast removal. The measurements will take place during their regular visits to the hospital for a medical check, so this study does not require extra hospital visits.

Group relatedness

This study is group-related, as it is evident that this study can be conducted only with participation of DRF-patients.

10.5 Compensation for injury*Insurance*

As the study has no risks, the Medical Ethical Committee of the UMCG decided to authorize dispensation from the statutory obligation to provide insurance (art. 4 paragraph 1 of 'Besluit verplichte verzekering bij medisch-wetenschappelijk onderzoek met mensen).

10.6 Incentives (if applicable)

The patients participating in this study do not receive any special incentives or financial compensation.

11. ADMINISTRATIVE ASPECTS AND PUBLICATION

11.1 Handling and storage of data and documents

The research data are handled and stored confidentially and anonymously. The principal investigator and study coordinator will have access to the source data. Only anonymous and not-personally-identifiable results of interim-analyses will be showed to other physicians and researchers who are not involved in this study. For publication purposes, also anonymous and not-personally-identifiable data will be used.

Questionnaires are stored in a cupboard in the office of the principal investigator. The principal investigator and study coordinator are the only persons who have access to this cupboard. Data files are stored on the personal account of the principal investigator and on the account of the study coordinator. These accounts are protected by passwords. The data will be stored for 5 years.

11.2 Amendments

Amendments are changes made to the research after a favourable opinion by the accredited METC has been given. All amendments will be notified to the METC that gave a favourable opinion.

11.3 Annual progress report

The sponsor/investigator will submit a summary of the progress of the trial to the accredited METC once a year. Information will be provided on the date of inclusion of the first subject, numbers of subjects included and numbers of subjects that have completed the trial, serious adverse events/serious adverse reactions, other problems, and amendments.

11.4 End of study report

The investigator will notify the accredited METC of the end of the study within a period of 8 weeks. The end of the study is defined as the last patient's last visit.

In case the study is ended prematurely, the investigator will notify the accredited METC, including the reasons for the premature termination.

Within one year after the end of the study, the investigator/sponsor will submit a final study report with the results of the study, including any publications/abstracts of the study, to the

accredited METC.

11.5 Public disclosure and publication policy

The investigators have nothing to disclose. The results of this study will be published in a peer reviewed scientific magazine.

